CDC	Centers for Disease Control
CFR	Code of Federal Regulations
CLIA	Clinical Laboratory Improvement Amendments
CLSI	Clinical Laboratory Standards Institute
CRF	Case Report Form
CRO	Contract Research Organization
CV	Curriculum Vitae
CV	Coefficient of Variation (relative standard deviation in %)
ERS	European Respiratory Society
FAS	Full Analysis Set
FeNO	Fractional Exhaled Nitric Oxide
FDA	Food and Drug Administration (U.S.)
GCP	Good Clinical Practices
HIPAA	Health Insurance Portability and Accountability Act
ICH	International Conference on Harmonization
ICS	Inhaled Corticosteroids
IFU	Instructions for Use
IRB/IEC	Institutional Review Board/Institutional Ethics Committee
ISF	Investigational Site File
µL	Microliter
mL	Milliliter
NAEPP	National Asthma Education and Prevention Program
NHLBI	National Heart, Lung, and Blood Institute
NICE	National Institute for Health and Care Excellence (UK)
NO	Nitric Oxide
OTC	Over-the-Counter
PI	Principal Investigator
POC	Point of Care
PPA	Positive Percent Agreement
SAE	Serious Adverse Event
SDV	Source Data Verification
SIV	Site Initiation Visit
TLC	Total Lung Capacity
TMF	Trial Master File
U.S.	United States
USB	Universal Serial Bus

STUDY SYNOPSIS

Name of Sponsor	Bosch Healthcare Solutions GmbH
Name of Device	Vivatmo pro TM (Bosch Healthcare Solutions GmbH)
Study Title	Clinical Study of the Vivatmo pro TM for Fractional Exhaled Nitric Oxide (FeNO) Monitoring of U.S. Asthmatic Patients Responding to Inhaled Corticosteroid (ICS) Treatment
Study Short Title	Vivatmo pro TM US Study
Study Type	Multi-center, open label, non-randomized, prospective, single cohort study
Number of Study Sites	6 clinical sites in the United States
Target Population	120 male and female asthma subjects from 7 to 80 years of age with uncontrolled asthma. Including: 
 ~40 subjects (~30%) from 7 to 17 years of age ~80 subjects (~70%) from 18 to 80 years of age
Study Objectives	
Primary Objective: To measure the impact of inhaled corticosteroid (ICS) treatment on fractional exhaled nitric oxide (FeNO) measured with the Vivatmo proTM in adult and pediatric subjects with uncontrolled asthma as measured at visits before and after treatment.
 
Secondary Objectives:
 
 To compare changes according to the primary objective with those of spirometry (lung function), and asthma symptoms before and after treatment. To evaluate the precision of repeat measurements made for each subject at a single visit. To evaluate the success rate of the subject using the device.
Study General Design and Duration	This is a multi-center, competitive enrollment, dual-visit, point-of-care study to evaluate fractional exhaled nitric oxide (FeNO) measured with the Vivatmo pro TM , spirometry, and asthma symptoms using an Asthma Control Questionnaire (ACQ) in adult and pediatric subjects. Subjects will be screened, enrolled and tested at Study Visit #1 and then prescribed inhaled corticosteroid (ICS) treatment as per routine clinical care. Subjects will return for Study Visit #2 in two weeks and repeat fractional exhaled nitric oxide

	
(FeNO) measured with the Vivatmo pro™, spirometry, and complete an Asthma Control Questionnaire (ACQ). Results of the first valid FeNO measurement made at each study visit (Visit #1 - pre-treatment and Visit #2 - post-treatment) will be analyzed in conjunction with recorded asthma symptoms and spirometry results. At least two FeNO measurements will be made at each visit allowing assessment of repeatability of the method under daily use conditions. Subject screening, recruitment, initial measurement, treatment, and follow up measurement are expected to take 3 months.

Study Endpoints	
Primary Endpoint: The primary analysis variable will be the percent change of the fractional exhaled nitric oxide (FeNO) measurement made at Visit #1 compared to Visit #2 using the Vivatmo pro™. The first valid FeNO measurement made at each visit will be used for this comparison analysis.
 
Secondary Outcome Measures:
 
 • The change in standard outcome measures (asthma symptoms and spirometry) between Visit #1 to Visit #2 • Repeatability as assessed by replicate FeNO measurements (N=2) at one or more visits. The first two valid FeNO measurements made for each subject at each visit will be used for this repeatability analysis. • Success rate (proportion of patients with successful measurement)
Subject Inclusion / Exclusion Criteria	
See criteria starting on page 23.

Study Procedures	
 Patients meeting study inclusion/exclusion criteria will be consented and will be enrolled in the study. Subjects will be observed during each of two study visits according to routine clinical diagnosis and treatment standards for uncontrolled asthma patients and will have asthma symptoms recorded using a standardized Asthma Control Questionnaire (ACQ). Subjects will have fractional exhaled nitric oxide (FeNO) and spirometry measured and documented at each visit. All study subjects will be asked to perform two valid fractional exhaled nitric oxide (FeNO) measurements at each study visit using the Vivatmo proTM with a limit of 10 total exhalation attempts per subject per visit. If only one valid measurement is taken, it will be used for comparative analysis. No repeatability data will be available for this subject. One operator will guide each subject through the fractional exhaled nitric oxide (FeNO) measurements at each visit. At the first visit, after all study assessments (FeNO, Spirometry, ACQ), subjects will receive therapy by prescription of inhaled corticosteroid (ICS) medication according to routine treatment standards. Subjects will return after 2 weeks (14 days) of treatment for a repeat of measurements.
Statistical Analysis	
Analysis Population:
 
The Full Analysis Set (FAS) will be defined as all patients intended to receive a FeNO measurement.
 
The Per Protocol Set will be defined as enrolled subjects without major protocol violations, with inhaled corticosteroid (ICS) treatment, and successfully completing at least one valid FeNO measurement at both Visit #1 and Visit #2 will be evaluated for the primary endpoint.
 
Definition of Measured Value:
 
For primary endpoint analysis the value of FeNO measurement will be derived as the result of the first valid measurement.
 
For repeatability, the first and second valid FeNO measurements at each visit will be used. Repeatability will be the pooled result of pairwise analyses for repeatability to demonstrate precision (see below).
 
Descriptive Statistics:
 
Baseline characteristics, such as demographics, as well as analytical clinical data by visit will be summarized using descriptive statistical methods.
 
Continuous data will be summarized using the mean, the median, standard

	
deviation, and range (minimum and maximum value). Categorical values will be summarized using frequency counts and percentages.
 
Analysis of Primary Endpoint: The change of FeNO values will be estimated in ANOVA with baseline values as the covariate and will be reported as percent change together with the 95%-confidence interval. In a sensitivity analysis, the first valid single measurement is used for the analysis.
 
Analysis of Secondary Endpoints: The relationship between changes in FeNO-values and clinical assessments (spirometry, ACQ-questionnaire) will be assessed by Spearman's rank correlation.
 
Repeatability: Repeatability will be estimated together with the 95%-confidence interval as pooled standard deviation (mean < 50 ppb) and CV (mean ≥ 50 ppb), respectively, using the residual variance component resulting from a random effects ANOVA (as used in CLSI EP05 guideline) with patient and visit as random factors.
 
The resulting pooled repeatabilities are hereby estimated taking into account conditions of variability over sites and operators.
 
Success rates: The success rates (proportion of patients with successful measurement within FAS) will be reported. The number of attempts necessary to obtain 2 valid replicate measurements will be tabulated in contingency tables by visit.
 
Sample Size: Since the effect size of the change (mean change / standard deviation) is on the order of 1 (resulting in N=10 and 13 for power = 80% and 90%, respectively) and therefore large, the sample size is not determined by the primary objective but by the necessity to achieve representative data of FeNO measurement data over all age groups, measurement ranges ($<$, \geq cut off) and sites. Thus, 120 subjects will be recruited.

--	--

TABLE OF CONTENTS

PROTOCOL REVISION HISTORY	3
PROTOCOL APPROVAL	3
PROTOCOL SIGNATURE PAGE	4
LIST OF ABBREVIATIONS	5
STUDY SYNOPSIS	6
TABLE OF CONTENTS	10
1. BACKGROUND AND INVESTIGATIONAL DEVICE	13
1.1. Background	13
1.2. Description of the Device	13
1.3. Intended Use	15
1.4. Special Conditions for Use Statement	16
1.5. Investigator Requirements	16
2. STUDY OBJECTIVES	16
2.1. Primary Objective	16
2.2. Secondary Objectives	17
3. STUDY DESIGN	17
3.1. General Design	17
3.2. Study Endpoints	17
3.3. Number of Subjects	18
3.4. Number of Study Sites	18

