8. DATA ANALYSIS AND STUDY ENDPOINTS

8.1. Analysis Populations

The Full Analysis Set (FAS) will be defined as all patients intended to receive a FeNO measurement.

The Per Protocol Set will be defined as enrolled subjects without major protocol violations, with inhaled corticosteroid (ICS) treatment, and successfully completing at least one valid FeNO measurement at both Visit #1 and Visit #2 will be evaluated for the primary endpoint.

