8.3. Analysis of Primary Endpoint

The change of FeNO values will be estimated in ANOVA with baseline values as the covariate and will be reported as percent change together with the 95%-confidence interval.

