8.4. Analysis of Secondary Endpoints

The relationship between changes of FeNO-values and clinical assessments (spirometry, ACQ-questionnaire) will be assessed by Spearman's rank correlation.

Repeatability will be estimated together with the 95%-confidence interval as pooled standard deviation (mean of measurement pair < 50 ppb) and CV (mean of measurement pair ≥ 50 ppb), respectively, using the residual variance component resulting from a random effects ANOVA (as used in CLSI EP05 guideline) with patient and visit as random factors. Technically, the CV is estimated as $100 \times$ standard deviation applying the random effects ANOVA on ln-transformed values. The resulting pooled repeatability is hereby estimated taking in account conditions of variability over sites and operators.

The *success rates* (proportion of patients with successful measurement within FAS) will be reported. The number of attempts necessary to obtain 2 valid replicate measurements will be tabulated in contingency tables by visit.

9. COMPLIANCE WITH GOOD CLINICAL PRACTICES (GCP), ETHICAL CONSIDERATIONS, AND ADMINISTRATIVE ISSUES

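### The planned sensitivity analysis uses the same first valid FeNO reading as the primary analysis, so it cannot differ from it, and section 8.3 has no sensitivity analysis

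*Combined protocol and SAP*

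**What the plan says.** **Primary value.** The synopsis (Study Endpoints) and section 3.2 use the same sentence: "The first valid FeNO measurement made at each visit will be used for this comparison analysis". The synopsis entry on the definition of the measured value repeats the rule: "For primary endpoint analysis the value of FeNO measurement will be derived as the result of the first valid measurement". The synopsis description of the general design agrees.

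**Primary model.** The synopsis and section 8.3 both state: "The change of FeNO values will be estimated in ANOVA with baseline values as the covariate". The result "will be reported as percent change together with the 95%-confidence interval".

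**Analysis set.** Section 8.1 describes the Per Protocol Set as subjects without major violations, on ICS treatment, and "successfully completing at least one valid FeNO measurement at both Visit #1 and Visit #2 will be evaluated for the primary endpoint". The Full Analysis Set is used only for the success rates: "proportion of patients with successful measurement within FAS) will be reported" (section 8.4).

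**Sensitivity analysis.** After the model sentence the synopsis adds: "In a sensitivity analysis, the first valid single measurement is used for the analysis". Section 8.3 ends without a counterpart, and sections 8.1, 8.2 and 8.4 contain none.

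**Second reading.** Under Study Procedures: "All study subjects will be asked to perform two valid fractional exhaled nitric oxide (FeNO) measurements at each study visit". The plan uses the second reading only for repeatability, and the number of attempts needed to obtain two valid readings is tabulated.

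**The concern.** A sensitivity analysis has to change something: the input, the model or the analysis set. The only feature stated for this one is its input, and that input is the primary one. An analyst following the synopsis will report the primary result twice, the second time labelled as a sensitivity analysis. An analyst following section 8.3 will report none. No other alternative analysis of the primary endpoint is planned, so the result has no prespecified check on either reading.

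The check has a purpose here. The primary endpoint rests on one reading per visit from a manoeuvre that depends on technique. Subjects are trained at Visit #1 and get a refresher at Visit #2 only if needed. A first-reading effect that differs between visits would bias the change, and an analysis of first readings alone cannot show it.

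**Working it through.** **1. The plan's own figure.** The synopsis gives N=10 and N=13 for 80% and 90% power at an effect size of about 1. A paired t-test with the noncentral t distribution and two-sided alpha 0.05 (assumed, since none is stated) gives N=10 (power 0.803) and N=13 (power 0.911). Both figures reproduce, and the point does not depend on them. At N=120 an effect size of 1 puts the mean change 1 × √120 ≈ 11 standard errors from zero, so the choice of reading is unlikely to alter the conclusion.

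**2. The two analyses side by side.**

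| | Primary | Sensitivity (synopsis) |
|---|---|---|
| FeNO value | first valid, each visit | first valid |
| Model | baseline-adjusted ANOVA | none other named |
| Analysis set | Per Protocol | none other named |

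The same input in the same model on the same subjects gives a difference of 0. As an illustration, take one simulated data set of 120 subjects (median baseline 40 ppb; ln SD 0.6; mean ln change −0.4 with SD 0.4; within-visit ln SD 0.1):

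- primary analysis: −37.568% (95% CI −42.079 to −32.707);
- sensitivity analysis as written: the same three numbers;
- mean of the two readings: −37.269% (−41.674 to −32.531).

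**3. What a mean-of-two analysis would show.** The documents give no within-visit SD and no scale for the primary model, so the following are assumptions: ln scale, within-visit SD e = 0.05 to 0.25, SD of true ln change s = 0.4 to 0.5, N = 120, and a share p of subject-visits with two valid readings.

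- Variance of a subject's change: s² + 2e² with first readings, s² + (2 − p)e² with the mean of two. SE ratio = √[(s² + (2 − p)e²)/(s² + 2e²)].
- SE of the difference between the two analyses = e√(p/N). The 95% band is exp(1.96 × SE) − 1.
- A first-reading shift d present at one visit only shows at p·d/2. The shift that falls outside the band in 80% of trials is exp[(1.96 + 0.84) × SE × 2/p] − 1.

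With p = 1:

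| e | SE reduction, s=0.4 / s=0.5 | SE of difference | 95% band | Shift seen in 80% of trials |
|---|---|---|---|---|
| 0.05 | 0.8% / 0.5% | 0.0046 | 0.9% | 2.6% |
| 0.10 | 2.8% / 1.9% | 0.0091 | 1.8% | 5.2% |
| 0.15 | 5.6% / 3.9% | 0.0137 | 2.7% | 8.0% |
| 0.25 | 11.6% / 8.7% | 0.0228 | 4.6% | 13.6% |

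Example, e = 0.25 and s = 0.4: √(0.2225/0.285) = 0.884, a reduction of 11.6%; 0.25/√120 = 0.0228; exp(1.96 × 0.0228) − 1 = 4.6%.

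With p = 0.9 the ranges are 0.4% to 10.4% (SE reduction), 0.9% to 4.3% (band) and 2.7% to 14.4% (detectable shift). With N = 100 and p = 1 the band is 1.0% to 5.0% and the detectable shift 2.8% to 15.0%.

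**4. Simulation** (5,000 trials, N = 120). The analysis as written minus the primary was 0 in every trial. For the mean of two, with e = 0.10 and s = 0.45, the band was exceeded in 5.2% of trials with no shift, 50.3% with a Visit #1 shift of 0.036 and 79.7% with one of 0.051. A shift of 0.10 at both visits gave a mean difference of 0.000: it cancels.

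**5. Reach.** With one group and baseline centred at its mean, the adjusted mean change equals the raw mean change. The band and detection figures therefore carry over to the planned model. The SE reductions are for the unadjusted change.

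**The case against.** The strongest case is that this is one redundant synopsis sentence. The study estimates a percent change with a confidence interval and sets no success threshold for a sensitivity analysis to protect. The primary input is stated consistently, so nobody running that analysis could be misled. Section 8.3 omits the sentence but does not contradict it. Deleting it would align the two places at no cost, and the mean-of-two replacement is partly a matter of preference.

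Much of this is fair. The primary result is not at risk, the mismatch with 8.3 is an omission, and the ranges above describe the replacement, not harm from the defect. But deletion would settle the mismatch by leaving the primary result with no check at all, when the sponsor evidently wanted one and the data will exist.

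A second objection is that the sensitivity analysis may have been meant for the Full Analysis Set, where it could differ by including subjects with major violations who have valid readings at both visits. The synopsis does not say so, and it names that set only for success rates. If that was the intention, it needs to be written down.

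A third is that the repeatability analysis in 8.4 already uses both readings, and a systematic first-to-second shift would inflate its residual variance. That is true, but the residual cannot separate a shift that differs between visits from ordinary noise, and only such a shift biases the change.

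**Conclusion.** The point holds. As written, the sensitivity analysis differs from the primary analysis by exactly 0, and section 8.3 has none. This rests on the text alone, given the same model and analysis set, and nothing in the documents names others. The consequence is limited: the primary estimate and the sample size stand, and the conclusion is unlikely to change, but the primary result has no working prespecified check. It should be corrected, though it does not threaten the trial.

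The replacement is modest. Under the assumed ranges at N=120 with two readings for all, it lowers the SE by 0.5% to 11.6% and reliably shows only visit-differential first-reading shifts of about 2.6% to 13.6% or more. It cannot show an order effect that is equal at both visits.

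**What to change.** Replace the synopsis sentence and put the same text in section 8.3, for example:

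> As a sensitivity analysis, the primary analysis is repeated with the mean of the first two valid FeNO readings at each visit (the one reading where only one is valid), using the same model and analysis set.

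The single-reading fallback agrees with the synopsis, which already lets a lone valid reading enter the comparison. If the sponsor intended something else, such as another analysis set, specify that in both places instead.

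Optionally, add to 8.4 the mean first-minus-second difference by visit with its 95% confidence interval, on the scales that section already uses (ppb for pair means below 50 ppb, ln for pair means of 50 ppb or more). This would show an order effect common to both visits.

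The cost is one replaced sentence in the synopsis, the same sentence in 8.3 and, if wanted, one more in 8.4. No new data, visits or subjects are needed.

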1. BACKGROUND AND INVESTIGATIONAL DEVICE

1.1. Background

According to the Centers for Disease Control (CDC) asthma has increased 28% in the last decade in the United States with the number of asthmatic individuals totaling 25 million adults (7.9% of the adult US population) and 6.1 million children (8.4% of US children). The National Institutes of Health (NIH) guidelines for the diagnosis and management of asthma strongly recommend long term anti-inflammatory therapy, such as oral or inhaled corticosteroids to reverse airway inflammation in an effort to prevent irreversible airway damage. The difficulty in diagnosing and managing asthma however lies primarily in the lack of available clinical technologies capable of assessing airway inflammation, an early and persistent component of asthma.

The medical community has expressed the need for objective and noninvasive measures of airway inflammation for diagnosing asthma and monitoring the effectiveness of and compliance with anti-inflammatory therapies. Because airway inflammation is a key pathophysiologic abnormality in asthma, there has been an emphasis on incorporating inflammatory biomarkers into the diagnosis and management of asthma.

Fractional exhaled nitric oxide (FeNO) as a noninvasive surrogate biomarker for airway inflammation can play a significant role in supporting asthma treatment and management decisions. Numerous studies have shown that fractional exhaled nitric oxide (FeNO) is well correlated with other markers of airway inflammation such as bronchial hyperresponsiveness, sputum eosinophils, bronchoalveolar lavage fluid eosinophilia, bronchial biopsy eosinophil score, and blood eosinophilia. Fractional exhaled nitric oxide (FeNO) levels have been shown to rise prior to asthma exacerbation and decrease with the use of anti-inflammatory medications in a dose dependent manner. Monitoring of fractional exhaled nitric oxide (FeNO) can help clinicians and patients with:

- Better self management⁽¹⁾
- Better safety⁽¹⁾
- Control of adherence⁽¹⁾
- Improved asthma control⁽²⁾
- Optimized steroid dosage⁽³⁾
- Reduction of exacerbations⁽⁴⁾
- Reduction of hospitalization⁽⁵⁾⁽⁶⁾
- Reduction of costs⁽⁵⁾

A new portable device using electrochemical sensors to measure fractional exhaled nitric oxide FeNO (Bosch Healthcare Solutions GmbH, Vivatmo *pro*TM) has recently been developed. The aim of this study is to evaluate the performance of this new hand-held device.

1.2. Description of the Device

The nitric oxide test system called the Vivatmo *pro*TM (Bosch Healthcare Solutions GmbH, Waiblingen Germany) is a point-of-care (POC) breath gas analyzer that uses solid-state electrochemical technology to measure fractional exhaled nitric oxide (FeNO), a biomarker for airway inflammation, in human exhaled breath. Measurement of FeNO is a quantitative and

non-invasive method to evaluate an asthma patient's response to anti-inflammatory therapy, as well as an adjunct to establishing a clinical assessment of asthma. The Vivatmo *pro*TM measures expired nitric oxide (NO) in the range of 5 ppb to 300 ppb from a 10 second exhalation. The Vivatmo *pro*TM is suitable for children 7 to 17 years of age and adults 18 to 80 years of age.

Vivatmo *pro*TM is comprised of two components: a handheld wireless measurement unit with disposable mouthpiece (held and used by the patient) and a base station with touch screen interface and AC adapter. The handheld mouthpiece is a single-patient use, disposable component used up to 5 times in a single testing session before being disposed of and replaced. The device keeps track of the number of uses for each mouthpiece. The mouthpiece has an ergonomically designed interface for the patient to aid in creating a proper seal during the exhalation maneuver. Vivatmo *pro*TM uses solid state, sensor technology sensitive to NO compounds in parts per billion (ppb) in the handheld component with a pneumotachograph display in the base station. The solid state sensor in the handheld component is preceded by filters in the disposable mouthpiece that: (a) eliminate germs and protect against cross-contamination; (b) eliminate potential interfering molecules such as carbon monoxide (CO), ammonia (NH₄), and methanol (CH₄O) by making them inactive; (c) convert breath NO to the NO₂ equivalent for measurement; and finally (d) dehumidify the breath sample. Vivatmo *pro*TM provides visual and audible feedback during the FeNO measurement process such that the user can modulate their breath speed within the optimal flow parameters as recommended by American Thoracic Society (ATS) and European Respiratory Society (ERS) standards.

To use the system the patient empties their lungs, inhales deeply to total lung capacity, and then slowly and evenly exhales through the Vivatmo *pro*TM mouthpiece of the handheld component for 10 seconds. Vivatmo *pro*TM tests the last three second fraction of a 10 second exhalation in order to report the average NO concentration in parts per billion (ppb). Results are processed and stored on the system using dedicated software. In order to verify the device's performance there are control procedures performed on a routine basis. Vivatmo *pro*TM also has an optional PC application for access and management of electronic testing records.

